6.3.4 Prohibited concomitant therapy

Concomitant use of sargramostim (GM-CSF), other anti-cancer therapies, including radiation, thalidomide, or other investigational agents is not permitted while subjects are receiving study drug during the treatment phase of the study.

7 Response Definition (see Appendix D + E)

7.1 Complete Response (CR)

- 7.1.1** Complete disappearance of all detectable clinical and radiographic evidence of disease and disappearance of all-disease related symptoms if present before therapy, and normalization of those biochemical abnormalities (e.g., lactate dehydrogenase [LDH] definitely assignable to NHL).
- 7.1.2** All lymph nodes and nodal masses must have regressed to normal size (≤ 1.5 cm in their greatest transverse diameter for nodes > 1.5 cm before therapy). Previously involved nodes that were 1.1 to 1.5 cm in their greatest transverse diameter before treatment must have decreased to ≤ 1 cm in their greatest transverse diameter after treatment, or by more than 75% in the sum of the products of the greatest diameters (SPD).
- 7.1.3** The spleen, if considered to be enlarged before therapy on the basis of a CT scan, must have regressed in size and must not be palpable on physical examination. However, no normal size can be specified because of the difficulties in accurately evaluating splenic and hepatic size. For instance, spleens thought to be of normal size may contain lymphoma, whereas an enlarged spleen may not necessarily reflect the presence of lymphoma but variations in anatomy, blood volume, the use of hematopoietic growth factors, or other causes. The determination of splenic volume or splenic index by CT scan is cumbersome and not widely used. Any macroscopic nodules in any organs detectable on imaging techniques should no longer be present. Similarly, other organs considered to be enlarged before therapy due to involvement by lymphoma, such as liver and kidneys, must have decreased in size.
- 7.1.4** If the bone marrow was involved by lymphoma before treatment, the infiltrate must be cleared on repeat bone marrow aspirate and biopsy of the same site. The sample on which this determination is made must be adequate (>20 mm biopsy core). Flow cytometry, molecular, or cytogenetic studies are not considered part of routine assessment to document persistent disease at the present time.

7.2 Complete Response/Unconfirmed (CRu)

CR/unconfirmed (CRu) includes those subjects who fulfill criteria 1 and 3 above, but with one or more of the following features:

7.2.1 A residual lymph node mass greater than 1.5 cm in greatest transverse diameter that has regressed by more than 75% in the SPD. Individual nodes that were previously confluent must have regressed by more than 75% in their SPD compared with the size of the original mass.

7.2.2 Indeterminate bone marrow (increased number or size of aggregates without cytological or architectural atypia).

7.3 Partial Response (PR)

7.3.1 $\geq 50\%$ decrease in SPD of the six largest dominant nodes or nodal masses. These nodes or masses should be selected according to the following features: (a) they should be clearly measurable in at least two perpendicular dimensions, (b) they should be from as disparate regions of the body as possible, and (c) they should also include mediastinal and retroperitoneal areas of disease whenever these sites are involved.

7.3.2 No increase in the size of the other nodes, liver, or spleen.

7.3.3 Splenic and hepatic nodules must regress by at least 50% in the SPD.

7.3.4 With the exception of splenic and hepatic nodules, involvement of other organs is considered assessable and not measurable disease.

7.3.5 Bone marrow assessment is irrelevant for determination of a PR because it is assessable and not measurable disease; however, if positive, the cell type should be specified in the report, e.g., large-cell lymphoma or low-grade lymphoma (i.e., small, lymphocytic small cleaved, or mixed small and large cells.)

7.3.6 No new sites of disease.

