3.4 Guidelines for Evaluation of Measurable Disease

- **Clinical lesions** will only be considered measurable when they are superficial (e.g skin nodules, palpable lymph nodes).
- **Chest X-ray** lesions are acceptable as measurable lesions when they are clearly defined and surrounded by aerated lung. However, CT is preferable.
- **Conventional CT and MRI** should be performed with cuts of 10mm or less in slice thickness contiguously. Spiral CT should be performed using a 5mm contiguous reconstruction algorithm. This applies to the chest, abdomen, and pelvis. Head & neck and extremities usually require specific protocols.
- **Ultrasound** should not be used to measure tumor lesions that are clinically not easily accessible when the primary endpoint of the study is objective response evaluation. It is a possible alternative to clinical measurements of superficial palpable nodes, subcutaneous lesions and thyroid nodules. US might also be useful to confirm the complete disappearance of superficial lesions usually assessed by clinical examination
- **PET/CT** may be performed as an alternative to CT or MRI at the investigator's discretion

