4.1 Inclusion Criteria

- **Documentation of disease**
 - Previously treated, histological confirmed follicle center lymphoma, grade 1-3a, marginal zone lymphoma, small lymphocytic lymphoma with < 5000 lymphocytes /mm³ or lymphoplasmacytic lymphoma with <3gm/ml IgM, mantle cell lymphoma by WHO classification (see Appendix F).
 - Bone marrow biopsies as sole means of diagnosis are not acceptable. Fine needle aspirates are not acceptable.
 - Institutional flow cytometry or immunohistochemistry must document CD20 antigen expression. Past documentation of CD20 antigen expression is admissible.
- **Prior treatment**
 - Patients must have been treated with rituximab in combination with chemotherapy or as monotherapy and must have refractory or progressive disease. Subjects must have had less than a partial response or progressive disease within 6 months of any dose of rituximab.
- Age ≥ 18
- ECOG performance status 0-2 (see Appendix B)
- Measurable disease must be present either on physical examination or imaging studies. Non-measurable disease alone is not acceptable. Any tumor mass $> 2\text{cm}$ is considered measurable.
- Lesions that are considered non-measurable, but assessable include the following:
 - Bone lesions (lesions if present should be noted)
 - Ascites
 - Pleural/pericardial effusion
 - Lymphangitis cutis/pulmonis
 - Bone marrow (involvement by non-Hodgkin lymphoma should be noted)
- Patients with a history of intravenous drug abuse or any behavior associated with increased risk of HIV infection should be tested for exposure to the HIV virus.

- Understand and voluntarily sign an informed consent form.
- Able to take aspirin (81 or 325 mg) daily as prophylactic anticoagulation. Patients intolerant to ASA may use warfarin or low molecular weight heparin
- Laboratory test results within these ranges:
 - Absolute neutrophil count $\geq 1000/\text{mm}^3$
 - Platelet count $\geq 75,000/\text{mm}^3$
 - Serum creatinine $\leq 2.0 \text{ mg/dL}$
 - Total bilirubin $\leq 1.5 \text{ mg/dL}$ (unless due to Gilbert's syndrome)
 - AST (SGOT) and ALT (SGPT) $\leq 2.5 \times \text{ULN}$ or $\leq 5 \times \text{ULN}$ if hepatic metastases are present.
- Disease free of prior malignancies for ≥ 5 years with exception of currently treated basal cell or squamous cell carcinoma of the skin, or carcinoma "in situ" of the cervix or breast.

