7.6 Progressive Disease (PD)

- 7.6.1 $\geq 50\%$ increase from nadir in the SPD of any previously identified abnormal node for PRs or non-responders.
- 7.6.2 Appearance of any new lesion during or at the end of therapy which is > 1.5 cm by radiologic evaluation or greater than 1 cm by physical examination.

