Appendix F: WHO classification of B-NHL

- Chronic lymphocytic leukemia/Small lymphocytic lymphoma
- B-cell prolymphocytic leukemia
- Lymphoplasmacytic lymphoma/Waldenström macroglobulinemia
- Splenic marginal zone lymphoma
- Plasma cell neoplasms
 - Plasma cell myeloma
 - Plasmacytoma
 - Monoclonal immunoglobulin deposition diseases
 - Heavy chain diseases
- Extranodal marginal zone B cell lymphoma (MALT lymphoma)
- Nodal marginal zone B cell lymphoma
- Follicular lymphoma
- Mantle cell lymphoma
- Diffuse large B cell lymphoma
- Mediastinal (thymic) large B cell lymphoma
- Intravascular large B cell lymphoma
- Primary effusion lymphoma
- Burkitt lymphoma/leukemia
- Lymphomatoid granulomatosis

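### A mass in an organ other than liver or spleen can be a patient's only measurable lesion at entry, yet Section 7 has no partial-response or growth-progression rule for it

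*Combined protocol and SAP*

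**What the plan says.** **At entry.** Section 4.1 states: "Measurable disease must be present either on physical examination or imaging studies. Non-measurable disease alone is not acceptable". It sets the threshold at any tumour mass above 2 cm, with no restriction to nodes. Its list of non-measurable lesions covers bone, ascites, effusions, lymphangitis and marrow, and includes no solid organ mass. Section 3.4 says that clinical lesions "will only be considered measurable when they are superficial (e.g skin nodules, palpable lymph nodes", and that chest X-ray "lesions are acceptable as measurable lesions when they are clearly defined and surrounded by aerated lung". Marginal zone lymphoma is eligible without a nodal requirement, and Appendix F, to which 4.1 refers, lists "Extranodal marginal zone B cell lymphoma (MALT lymphoma".

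**At scoring.**
- PR (7.3.1) is a fall of at least 50% in the SPD of up to six nodes or nodal masses. Section 7.3.3 adds a size rule for splenic and hepatic nodules. Section 7.3.4 closes the list: "With the exception of splenic and hepatic nodules, involvement of other organs is considered assessable and not measurable disease".
- CRu by size (7.2.1) concerns a residual nodal mass.
- PD by growth (7.6.1) is a 50% or greater "increase from nadir in the SPD of any previously identified abnormal node for PRs or non-responders". PD by new lesion (7.6.2) applies at any site.
- SD (7.4.1) is whatever is neither PR nor PD.
- Growth at earlier sites of disease is mentioned in 7.5.1, but only for patients who reached CR.

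**Response rates.** Section 7.8.1 (Part I) counts CR, CRu and PR. Section 7.8.2 (three months after rituximab) counts CR, CRu, PR and SD.

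**The concern.** The plan uses one definition of measurable disease to admit patients and a narrower one to score them. A patient can satisfy 4.1 on a lesion whose shrinkage or growth Section 7 then never measures. Applied exactly as written, the criteria put a large shrinkage and a large growth of the same lesion in the same category, SD.

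Response rate is the primary objective (2.1.1), and the trial is open-label and single-centre. If readers fill the gap by judgement, the scoring depends on unwritten rules that 7.3.4 contradicts. If they follow the text, the Part I response rate, the post-rituximab response rate, TTP and PFS can all be wrong for these patients, and not all in the same direction.

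**Working it through.** **1. Does any clause rescue the patient?** Take a patient whose only measurable lesion is a lung mass of 5 × 4 cm (product 20 cm²). The dimensions are illustrative.

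| Change | Product | Relative change | Rules tried | Score |
|---|---|---|---|---|
| Shrinks to 2 × 2 cm | 4 cm² | (4 − 20)/20 = −80% | CR fails (7.1.3, nodule still present); CRu fails (7.2, same reason, and the residue is not nodal); PR fails (7.3.1, 7.3.4) | SD |
| Grows to 8 × 6 cm, no new lesion | 48 cm² | (48 − 20)/20 = +140% | 7.6.1 fails (not a node); 7.6.2 fails; 7.5.1 applies only after CR | SD |
| Disappears | 0 | −100% | 7.1.1 and 7.1.3 met | CR, if the other CR criteria are met |

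Appendix D repeats the nodal rules. Appendix E scores physical examination, nodes, node masses and marrow, and names liver or spleen changes and new sites. It has no entry for an existing mass in another organ. Marrow findings can still change the category once the mass is gone: CRu through 7.2.2, or PR through the positive-marrow row of Appendix E. Neither measures the mass.

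The liver and spleen exception belongs to PR only. Section 7.6.1 does not mention those nodules, although Appendix E lists an enlarging liver or spleen as progression.

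**2. Direction of the error, endpoint by endpoint.**

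| Endpoint | True partial shrinkage scored SD | True growth scored SD |
|---|---|---|
| 7.8.1, CR/CRu/PR | response lost, rate too low | no effect |
| 7.8.2, CR/CRu/PR/SD | no effect | counted as response, rate too high |
| CR/PR analyses (e.g. albumin, 2.2.7) | responder classed as non-responder | no effect |
| TTP, PFS (7.9, 7.10) | no direct effect | event missed, times too long |

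**3. Size per patient.** One misclassified patient moves a rate by 1/N: 1/45 = 2.2 points, 1/25 = 4.0 points, 1/20 = 5.0 points. These denominators are approximate. Section 7.8.1 counts everyone given one day of treatment, 7.8.2 only those given rituximab, and Section 8 allows replacement of non-evaluable subjects.

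**4. The plan's power figure, and an illustration.** Section 8 gives 87% power for McNemar's test: 10% against 35%, kappa 0.10, N = 45. Alpha is not stated for this test; I assume two-sided 0.05.

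- Chance agreement: 0.10 × 0.35 + 0.90 × 0.65 = 0.620.
- Agreement with kappa: 0.620 + 0.10 × 0.380 = 0.658.
- Discordance: 1 − 0.658 = 0.342. The difference is 0.25.
- Discordant cells: (0.342 + 0.25)/2 = 0.296 and (0.342 − 0.25)/2 = 0.046.
- Enumerating the uncorrected test gives 87.3%, so the stated figure reproduces.

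Section 8 does not say which response definition this test uses. Suppose it is CR/CRu/PR, a share f of patients has only such a mass, a share c of their responses is CR (still scoreable), and the baseline 10% is unaffected. The observed rate is then 0.35(1 − f) + 0.35fc. Both f and c are assumptions.

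| f | Rate, c = 0 | Power | Rate, c = 0.3 | Power |
|---|---|---|---|---|
| 5% | 33.3% | 82.6% | 33.8% | 84.2% |
| 10% | 31.5% | 76.9% | 32.6% | 80.5% |
| 20% | 28.0% | 62.8% | 30.1% | 71.7% |
| 30% | 24.5% | 46.4% | 27.7% | 61.3% |

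Under the 7.8.2 definition this loss does not arise. The error there is upward, from growth.

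**The case against.** **These are workshop criteria, adopted on purpose.** Appendix D presents them as such, and a nodal emphasis is a legitimate choice. But the protocol widened measurability itself in 3.4 and 4.1 without carrying that into scoring. The objection explains where the scoring wording came from; it does not remove the contradiction.

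**Few patients may be affected.** This stands. The documents give no count. Appendix F is a general list that also contains ineligible entities, so it shows that an extranodal-only patient is possible under the eligible histologies, not that one enrolled.

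**Most extranodal disease is still scoreable.** This also stands. Patients with measurable nodes are scored on those, and CR and new-lesion PD remain available. For a soft-tissue mass that is not organ involvement, 7.3.4 is less clear, so the lung mass is the cleaner example.

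**Stronger readings that do not hold.** A reader might infer that the gap lowers every response rate, including the one for lenalidomide plus rituximab. Section 7.8.2 counts SD, so a PR scored as SD leaves that rate unchanged, while unscored growth raises it. A reader might also infer a biased comparison between cohorts through differing histology. Section 8 plans within-patient comparisons on 45 subjects and specifies no between-cohort test; the synopsis mentions Fisher's exact test without naming groups.

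**Conclusion.** The concern holds for patients whose only measurable lesion is an extranodal mass outside liver and spleen. The wording conflict is certain; its effect on the results is not, because the number of such patients is unknown. For each one, partial shrinkage is lost from the Part I rate and from CR/PR analyses, growth is counted as a response under 7.8.2, and TTP and PFS miss the growth event. The shift per patient is about 2 points with a denominator near 45, or 4 to 5 points within a cohort of 25 or 20. The power losses above are illustrations: they rest on assumed shares and on response meaning CR/CRu/PR, and the plan's 87% is not itself in error. The point warrants correction because a stated rule gives a wrong score and the remedy is cheap.

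**What to change.** Use one definition of measurable disease for endpoint scoring across Sections 3.4, 4.1, 7.2, 7.3 and 7.6 and Appendices D and E, so that every lesion accepted as measurable at entry has a PR and a growth-PD size rule:

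- In 7.2.1, 7.3.1, 7.6.1 and Appendix D, extend the nodal terms to extranodal masses that meet 4.1 and can be measured in two perpendicular diameters.
- State in 7.6.1 how splenic and hepatic nodules are handled.
- Restrict 7.3.4 to the lesions that 4.1 lists as non-measurable.
- Add the corresponding entries to the Appendix E table.
- Reconcile the passages that tie withdrawal to progression (3.1, 4.4, 7.8.1) with the aligned definition.

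For subjects already enrolled, re-score from existing images where two-dimensional measurements can be obtained. Report results under both the current and the aligned wording, and label the re-scoring post hoc: Section 8 shows that responses in the first eleven patients had already been examined.

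**Cost.** A wording amendment, possibly some re-measurement of existing scans, and a small departure from the workshop text that must be stated. No new imaging is needed. Because 7.3.4 calls these lesions not measurable, two-dimensional measurements may not have been recorded, and a skin lesion followed only by examination may not be recoverable.

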7.4 Stable Disease (SD)

7.4.1 Stable disease is defined as less than a PR (see above) but is not progressive disease (see below).

7.5 Relapsed Disease (RD)

- 7.5.1 Appearance of any new lesion or increase by $\geq 50\%$ in the size of previously involved sites. (only applies to subjects that achieve a CR).
- 7.5.2 $\geq 50\%$ increase in greatest diameter of any previously identified node greater than 1 cm in its short axis or in the SPD of more than one node.

7.6 Progressive Disease (PD)

- 7.6.1 $\geq 50\%$ increase from nadir in the SPD of any previously identified abnormal node for PRs or non-responders.
- 7.6.2 Appearance of any new lesion during or at the end of therapy which is > 1.5 cm by radiologic evaluation or greater than 1 cm by physical examination.

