1.4 Rationale

Based on these vitro and in vivo studies, we propose to evaluate the potential of lenalidomide to overcome rituximab resistance. As pre-clinical data and published clinical data suggest a synergistic effect between lenalidomide and dexamethasone, we propose initial treatment with both drugs for two 28-day treatment cycles (Part I or “priming”) for subjects enrolled to Cohort 1. This combination in itself should have clinical efficacy. The priming phase in Part I will allow the study of immune-modulatory effects on T-cell subsets and cytokine milieu induced by the combination of lenalidomide and dexamethasone prior to the addition of rituximab. A reduced dose of lenalidomide 10 mg daily was chosen as the starting dose, given the heavily pre-treated patient population and the potential for lenalidomide-related myelosuppression. After the first lenalidomide – dexamethasone treatment cycle, the lenalidomide dose can be increased by one dose level based on patient-specific tolerance (see Section 6 for full details). After response assessment following two cycles of lenalidomide – dexamethasone, patients with responsive or stable disease, and patients with progressive disease with an estimated life expectancy of > 3 months will enter Part II with lenalidomide - dexamethasone and rituximab to evaluate the potential reversal of rituximab resistance as measured by response to rituximab and progression-free survival following rituximab.

Subjects enrolled to Cohort 2 of protocol treatment will receive treatment on the same schedule as those subjects in Cohort 1 (10 mg lenalidomide daily, weekly rituximab during Cycle 3), but

weekly dexamethasone will be eliminated from the study treatment plan. Response assessments will be conducted at the same timepoints (at the end of cycles 2 and 5).

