3.1 General Design

Phase II Trial of Lenalidomide (Revlimid[®]) + Rituximab with and without Dexamethasone in recurrent small B cell non-Hodgkin lymphomas (NHL) resistant to Rituximab:

[^] Close monitoring for tumor lysis syndrome (TLS) should be initiated concurrent with the initiation of lenalidomide-dexamethasone in Part I (see Section 3.2). Subjects will receive tumor lysis prophylaxis if clinically indicated. All subjects should remain well hydrated during at least the first 7 days of Cycle 1. Close monitoring for TLS and the need for TLS prophylaxis should be repeated during at least the first 7 days of Part II treatment. Additional TLS monitoring and prophylaxis may be employed at any time at the investigator's discretion. Tumor flare occurring during the first 1-2 weeks of Cycles 1, 2 and 3 should be recorded as AEs and not as progressive disease (PD). Tumor flare should be treated symptomatically with non-steroidal anti-inflammatory agents (NSAIDs) and other measures as needed

* Follow-up staging 3 months after first dose of Rituximab (i.e after 5 months) then after months 12, 18 and 24 (as counted from enrollment of trial), then yearly until disease progression, development of unacceptable toxicity, or voluntary withdrawal, whichever occurs first.

† In patients with absolute lymphocyte count >20,000/ μ l, prior to rituximab infusion, close monitoring for tumor lysis syndrome should be initiated and those patients should receive appropriate supportive care (e.g., allopurinol, intravenous hydration, additional laboratory test monitoring, etc.). A modified dosing scheme is suggested for those patients with absolute lymphocyte count >20,000/ μ l (see 6.2)

At time of progression or relapse, a biopsy is recommended. If a biopsy is performed, and the patient consented to allow their tissue to be kept for future unknown use, the pathology specimen will be asservated at the U Penn Tissue Core facility.

Subjects with CR, PR, SD or PD with an estimated life expectancy of >3 months will continue to Part II of the trial

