7.9 Time to progression (TTP)

TTP is defined as the time from the first day of protocol therapy to the first event defining progression of disease or last subject contact. TTP is defined for all subjects receiving protocol therapy, following an intent-to-treat analysis plan. TTP from rituximab is defined for patients receiving rituximab (Part II) from the first day of rituximab therapy to the first event defining treatment failure.

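### Part II has no reference scan of its own, so subjects who progressed in Part I can be scored as failing rituximab because of growth that came before it

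*Combined protocol and SAP*

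**What the plan says.** Section 3.1 sets who moves on: "Subjects with CR, PR, SD or PD with an estimated life expectancy of >3 months will continue to Part II of the trial". Section 1.4 repeats it ("patients with progressive disease with an estimated life expectancy of > 3 months will enter Part II") and gives the purpose of Part II: "to evaluate the potential reversal of rituximab resistance as measured by response to rituximab and progression-free survival following rituximab".

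The lesion rules in Section 7 are written once for the whole study:

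- **PD by size (7.6.1):** at least a 50% "increase from nadir in the SPD of any previously identified abnormal node for PRs or non-responders".
- **PD by new lesion (7.6.2):** "Appearance of any new lesion during or at the end of therapy", above a size limit.
- **PR (7.3):** at least a 50% "decrease in SPD of the six largest dominant nodes or nodal masses", with no reference scan named, and "No new sites of disease", with no date from which new is judged.
- **Part II response rate (7.8.2):** CR, CRu, PR or SD three months after rituximab, among subjects who received it.
- **TTP from rituximab (7.9):** "from the first day of rituximab therapy to the first event defining treatment failure". Treatment failure is not defined.
- **PFS from rituximab (7.10):** a secondary calculation that moves the start date only.

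Appendix D repeats the lesion rules. Sections 3.1 and 3.3 require restaging between Part I and Part II, but nothing makes that scan the Part II reference.

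**The concern.** For the rituximab endpoints the clock restarts at Part II and the lesion measurements do not. Scheduled imaging before rituximab consists of the entry scan and the end-of-Part-I scan. For a subject who progressed by size in Part I, the imaging nadir is therefore the entry scan. At the first scan after rituximab, that subject is judged against a value that was already exceeded by 50% or more before the first infusion.

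The subjects concerned are those whose disease grew on lenalidomide, with or without dexamethasone, and who were kept on study to see whether adding rituximab helps. If disease control after rituximab is recorded as progression, TTP and PFS from rituximab are biased downward in this group. The first Part II scan falls three months after the first infusion, so such a failure would be recorded at about three months. Because PR and new sites carry no reference, two assessors could also score the same scans differently.

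**Working it through.** **The plan's own figure.** No stated number is in dispute. The nearest is the 87% power for McNemar's test in Section 8 (45 patients, 10% versus 35%, kappa 0.10).

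- Chance agreement is 0.10 × 0.35 + 0.90 × 0.65 = 0.62.
- Observed agreement is 0.62 + 0.10 × 0.38 = 0.658, so discordance is 0.342. It splits into 0.296 and 0.046.
- Enumerating the discordant pairs with the uncorrected chi-square gives 87.3%, which reproduces the plan. Two-sided 0.05 is assumed; Section 8 states it only for the albumin analysis.

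**Leaving PD (7.6.1).** Set a node's entry SPD, taken as its nadir, to 1, and let it grow by a fraction g in Part I, to 1 + g. It stops meeting PD only below 1.5, so the shrinkage needed from the start of Part II exceeds 1 − 1.5/(1 + g).

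**Reaching PR (7.3.1).** This needs two assumptions: PR is read against entry, and the whole six-node SPD grew by g. The shrinkage needed is then 1 − 0.5/(1 + g). If only one of six equal nodes grew by g, the sum becomes 1 + g/6 and the requirement is 1 − 0.5/(1 + g/6).

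| Growth in Part I | To leave PD | PR, all six nodes grew | PR, one of six grew |
|---|---|---|---|
| 50% | more than 0% | 67% | 54% |
| 100% | more than 25% | 75% | 57% |
| 200% | more than 50% | 83% | 62.5% |

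Against the scan before Cycle 3, PR would need 50% in every row.

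**Worked cases (SPD at entry, after Part I, after rituximab).**

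- 100, 160, 155: 3% smaller since rituximab began (5/160), but above 150, so PD. Counted as progression in TTP and PFS from rituximab, and as a non-response in 7.8.2.
- 100, 200, 90: 55% smaller since rituximab began (110/200), but only 10% below entry. This is SD against entry and PR against the scan before Cycle 3. Section 7.8.2 counts it as a response either way; a CR/PR analysis such as the albumin one in Section 8 does not if PR is read against entry.
- 100, 160, 235: 47% larger since rituximab began (75/160) and 135% above entry. This is PD as written. Re-based to 160, the PD limit is 240, so it becomes SD and would count as a response under 7.8.2.

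**New lesions.** If new means new since entry, a lesion first seen in Part I bars PR for as long as it persists. CR is not barred, since it requires the lesion to disappear.

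**Sensitivity.** The number of Part I progressors is not given. If 1, 2, 3 or 4 responses of 45 were lost from the rate used in McNemar's test, 35% would fall to 32.8%, 30.6%, 28.3% or 26.1%, and power from 87.3% to 81.2%, 73.5%, 64.3% or 54.1%. These are illustrations, not estimates. Section 8 does not say which response definition enters that test.

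**The case against.** The strongest reply is that the text leaves a reference unstated but does not prescribe a wrong one. Several parts of that reply stand:

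- Section 7.8.2 counts SD, so that rate loses subjects only at the SD/PD boundary, or through how new lesions are read. The PR thresholds do not decide it.
- PD is judged on any single node and PR on a six-node sum. The 67%, 75% and 83% figures need the whole sum to have grown.
- Section 7.6.2 concerns a lesion's appearance. A lesion already seen before Cycle 3 did not appear after rituximab, so it need not end TTP from rituximab.
- The primary objective is response to the regimen, and an entry baseline is legitimate and conservative for that.

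A reader might infer that every Part I progressor is mis-scored, or that a new lesion in Part I makes PR impossible. The documents support neither. Nor do they support a count. An assumed 20% to 40% progressing and continuing would be 9 to 18 of 45, but no such share is given, and subjects who land in the same category under both references are unaffected. A reader might also credit any later shrinkage to rituximab. Lenalidomide continues through Part II and may have been escalated at Cycle 2, so a delayed lenalidomide effect is not excluded.

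The reply does not remove the size rule. Section 7.6.1 does name a reference, the nadir, and for a Part I size progressor on the scheduled scans that is the entry scan. The tumor-flare provision in Section 6.3.2 covers only the first one to two weeks of Cycles 1 to 3, not PD documented at restaging.

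**Conclusion.** The point holds in a limited form and should be fixed. On the literal text, a Part I size progressor who is stable or modestly smaller after rituximab can still be PD. TTP and PFS from rituximab can therefore record failure from earlier growth, and the subject is lost from the 7.8.2 rate at the SD/PD boundary. The size per subject is the shrinkage needed to leave PD: more than 0%, 25% or 50% after Part I growth of 50%, 100% or 200%. This rests on the entry scan being the nadir.

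The effect on PR is conditional on reading PR against entry, and it is smaller if only some nodes grew. It bears on CR/PR-based analyses, not on 7.8.2. The effect of new lesions depends on what new is taken to mean. The number of subjects affected cannot be derived from the documents. TTP and PFS from the first day of therapy are not in question.

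**What to change.** - **TTP and PFS from rituximab:** name the restaging scan before Cycle 3 as the reference. PD is at least a 50% increase from the lowest value at or after that scan, and a new lesion is one not present on it. Define treatment failure in Section 7.9 accordingly.
- **Part II response:** report CR/CRu/PR against that scan, separately from SD. Do not count re-based SD as response in subjects with PD at the end of Part I; otherwise the 100, 160, 235 case becomes a response.
- **Whole-regimen response, and TTP and PFS from the first day of therapy:** keep entry-baseline scoring. State in Section 7.3 which scan PR and new sites refer to.
- **Reporting:** show both scorings for Part I progressors, and say that shrinkage after rituximab cannot be attributed to rituximab alone.
- **Withdrawal:** Section 4.4 and the Study Summary remove subjects for progression after rituximab and use the same term. Those passages and Section 7 must be reconciled, because one scan could otherwise be PD for one purpose and not for the other.

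The cost is wording in Section 7, a second scoring of scans already taken, and two result columns for subjects who progressed in Part I. No extra imaging is needed.
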